#### FUNDING

# **VERSION DATE** 5/19/2017

### SPECIFIC AIMS

Concisely state the objectives of the study and the hypothesis being tested.

Inadequate response to antidepressant therapy in major depressive disorder (MDD) is disabling and highly prevalent, particularly among women. Although the use of antidepressant augmentation strategies is common, there are few effective therapies and few strategies that have been studied in a rigorous, controlled fashion.

Because studies in other female populations suggest that low-dose testosterone administration (in which testosterone levels are raised within the normal female range) has antidepressant effects with minimal side effects, testosterone is a candidate for a novel augmentation treatment for women with MDD. Preliminary studies from our group demonstrate antidepressant efficacy of low-dose testosterone administration in women with inadequate response to inhibitors of serotonin uptake, as well as in other female relatively androgendeficient populations. We propose to test the efficacy and tolerability of testosterone as an augmentation treatment for depressed women with inadequate response to antidepressant therapy in a randomized, placebo-controlled trial, which, if positive, will form the basis of a future, large, randomized, controlled trial.

An additional potential benefit of testosterone therapy is that it targets two specific persistent/residual symptoms of MDD – fatigue and sexual dysfunction. Fatigue/loss of energy and reduced libido/sexual function are common symptoms associated with MDD and ones for which few effective therapies are available. Moreover, data suggest that libido and sexual function may be independently and adversely affected by antidepressant therapy administration in a substantial subset of women. Our preliminary data suggest that low-dose testosterone may be an effective therapy for these two target symptoms in depressed women with partial/nonresponse to antidepressant therapy. In addition, data suggest that low-dose testosterone therapy increases energy and improves libido and sexual function in women. However, the specific therapeutic potential of low-dose testosterone augmentation has not been tested with a randomized, placebo-controlled study in MDD women with inadequate response to antidepressant therapy.

Rigorous, randomized, placebo-controlled trials are necessary to determine whether lowdose testosterone augmentation will be an effective treatment for depression in women with inadequate response to antidepressant **therapy**. In this application, a double-blind, placebocontrolled trial of adjunctive low-dose testosterone for inadequate response to antidepressant **therapy** among MDD women is proposed.

*Specific Aim 1*. Low-dose testosterone augmentation improves depressive symptoms in women with MDD and partial/nonresponse to antidepressant therapy.

*Aim 1A.* We will investigate in female antidepressant therapy partial/nonresponders whether low-dose testosterone augmentation for 8 weeks leads to a significantly greater reduction in depressive symptoms than placebo.

*Aim 1B.* We will investigate whether a key mechanism underlying the effects of testosterone administration on depressive symptoms is an increase in neuroactive testosterone metabolites, including 3alpha-diol.

*Specific Aim 2.* Adjunctive low-dose testosterone is safe and well-tolerated in women with MDD and partial/nonresponse to antidepressant therapy. We will investigate whether low-dose testosterone augmentation therapy for 8 weeks is safe and well-tolerated in female antidepressant therapy partial/non-responders compared to placebo.

*Specific Aim 3.* Low-dose testosterone augmentation improves two specific RDoC construct symptoms (in the Arousal/Physiologic Processes Domain) in women: fatigue and sexual dysfunction. We will investigate in female antidepressant therapy partial/nonresponders whether low-dose testosterone augmentation for 8 weeks improves associated fatigue and sexual dysfunction compared to placebo.

*Specific Aim 4.* Low-dose testosterone therapy in women with treatment resistant depression will cause functional changes in the brain. We will investigate the mechanisms and functional neuroanatomy of the effects of testosterone on different regions of the brain in women with treatment resistant depression. This will serve as preliminary data for future studies and grants.

*Exploratory Aim:* We will investigate androgen and other hormonal correlates of functional and structural neuroanatomy in women with treatment resistant depression compared with healthy, non-depressed controls. This will serve as preliminary data for future studies.

# Specific Aim 5. Androgen and neuroactive steroid levels will be lower in postmenopausal women with treatment resistant depression than in healthy controls.

We will investigate androgen and neuroactive steroid levels in postmenopausal women with treatment resistant depression in comparison to androgen and neuroactive steroid levels in postmenopausal healthy controls without significant psychiatric disease.

# BACKGROUND AND SIGNIFICANCE

Provide a brief paragraph summarizing prior experience important for understanding the proposed study and procedures.

Although a number of potential augmentation strategies for MDD patients with partial/nonresponse to antidepressant therapy have been studied, few have been shown to be effective and fewer have acceptable side-effect profiles. The development of low-dose physiologic testosterone therapy for women is an innovative and potentially important approach to the prevalent problem of partial/nonresponse to antidepressant therapy among women with MDD. This is an approach that has never been pursued previously in any double-blind, randomized fashion. Furthermore, examination of the effects of experimental manipulation of peripheral gonadal hormone concentrations on RDoC candidate constructs (anergia/fatigue and sexual dysfunction) within the domain of Arousal/Regulatory Processes reflects an innovative approach. The RDoC perspective we propose involves focus on these constructs independent of depression diagnosis, to generate data that may contribute to a larger body of findings supporting new ways of classifying mental disorders based on observable behavior and neurobiological measures. The classic gonadal steroid dichotomous paradigm (estrogens as the female hormone/testosterone as the male hormone) has only recently been understood to be an oversimplified framework. Although testosterone levels in women (and estrogen levels in men) are much lower than that in the opposite sex, there is increasing evidence that their role in the regulation of brain function may be important. This new area of investigation is an innovative approach that may have important clinical implications and may identify new potential targets for drug development in MDD. Investigation of neuroactive, GABAergic steroid metabolites of testosterone as a possible mechanism responsible for brain effects is another innovative component.

Partial/nonresponse to antidepressant **therapy** is extremely prevalent in the U.S., disproportionally affects women, and is associated with substantial morbidity and functional impairment. An effective, well-tolerated therapy would have a significant impact on public health. Antidepressant treatments with novel mechanisms of action and benign side effect profiles are needed. Preliminary data suggest that low, physiologic doses of testosterone may be effective to improve mood among women with partial/nonresponse to antidepressant therapy, yet with few side effects. If these preliminary findings are confirmed, results from the proposed study would form the basis for a larger, multi-center trial with active comparators to definitively establish that low-dose testosterone augmentation in women with antidepressant therapy partial/non-response is effective, well tolerated and exerts durable effects on mood in antidepressant-treated women with MDD, through effects on neuroactive steroids.

#### **RESEARCH DESIGN AND METHODS**

Briefly describe study design and anticipated enrollment, i.e., number of subjects to be enrolled by researchers study-wide and by Partners researchers. Provide a brief summary of the eligibility criteria (for example, age range, gender, medical condition). Include any local site restrictions, for example, "Enrollment at Partners will be limited to adults although the sponsor's protocol is open to both children and adults."

**Study Design:** After antidepressant therapy partial or nonresponse is established by documentation of failure to at least 8 weeks' treatment with an adequately dosed antidepressant therapy, A minimum of 100 subjects study-wide (60 from MGH) with MADRS $\geq$ 12 will enter the double-blind augmentation randomized-placebo-controlled treatment study. 50 of these subjects will be on active study drug and 50 will be control subjects on placebo. Eligible subjects will undergo baseline assessment of symptoms and biological measures and then be randomized to 1 of 2 groups: low-dose physiologic testosterone augmentation by transdermal preparation or placebo.

Antidepressant dose will be held steady during the trial. Outcome measures will examine the antidepressant efficacy of physiologic testosterone treatment (Aim 1), its tolerability (Aim 2) and its effects on 2 specific RDoC symptoms (Aim 3).

**Subject Enrollment:** A total of 330 women will be enrolled study-wide, of which 100 women with antidepressant-resistant MDD and 50 women with no psychiatric history will be eligible study-wide. Study subjects for the depressed population will be women, ages 21-75 with failure to remit following at least 8 weeks antidepressant trial documented by past treatment history.

In addition, 20 healthy controls without

depression will be recruited for the fMRI substudy healthy control population.

Up to 60 postmenopausal women who do not have current or past psychiatric disorders will also be screened to obtain 30 women who will be enrolled

as healthy controls.

Randomized Study Subject Population (n=60)

Inclusion Criteria for Randomized Study Subjects:

- 1. Female, age 21-75, who provide written informed consent
- 2. Free testosterone level no higher than the third quartile of the normal range
- 3. Meet DSM-IV criteria (by SCID) for current Major Depressive Disorder and have MADRS≥12
- Currently treated with an antidepressant (1st, 2nd or 3rd trial in current episode), that has been taken at an adequate dose for at least eight weeks with sufficient source documentation to confirm high level of confidence in treatment details (using the MGH ATRQ). Current treatment may include a combination therapy as long as the subject has not exceeded three failed trials in the current episode.
- 5. Persistent depression symptom burden of the same dose of the currently (ineffective) antidepressant therapy, evidenced by MADRS≥12.

Exclusion Criteria for Randomized Study Subjects:

- 1. Serious suicide or homicide risk, as assessed by evaluating clinician
- 2. Unstable medical illness including cardiovascular, hepatic, renal, respiratory, endocrine, neurologic
- 3. Substance use disorder active within last six months, or clinical suspicion of ongoing substance use disorder at the discretion of the study clinician at time of screening based on history and/or laboratory results.
- 4. Any history of psychotic features, bipolar disorder, or primary obsessive compulsive disorder, as assessed by SCID
- 5. Untreated hypothyroidism. If treated hypothyroidism, change in levothyroxine dose within the prior 3 mos
- 6. Use of androgens, including testosterone, DHEA and methyltestosterone, within the prior three months
- 7. Any investigational psychotropic drug within the last 30 days
- 8. In the judgment of the study clinician, unlikely to be able to participate safely throughout the study period (three or more episodes of self-harm in the past year, documented history of poor treatment adherence, or frequent missed appointments (>50%) in the past year)
- 9. Alanine aminotransferase (ALT) > 3x upper limit of normal or creatinine> 3x upper limit
- 10. History of a hormone-responsive cancer
- 11. History of testosterone abuse
- 12. Almond allergy (AndroFeme contains almond oil)
- 13. History of hypercalcemia or thromboembolism
- 14. Women who are breastfeeding
- 15. Pregnant women, women who desire to become pregnant, or women of child bearing potential who are not using a medically accepted means of contraception (to include condom, diaphragm, spermicide, intrauterine device, tubal ligation, or partner with vasectomy)

Additional Exclusion Criteria for Randomized study subjects in fMRI Substudy Only (n=20)

Exclusion criteria for the fMRI substudy participants include routine MRI exclusion criteria as listed below:

- Cardiac pacemaker
- Surgical aneurysm clips
- Neurostimulator
- Implanted pumps
- Metal fragments in body / eyes
- Pregnancy
- Nitroglycerin patch (if non-removable)
- Weight >250
- Severe claustrophobia

Healthy Control fMRI Population (n=20)

Inclusion criteria for fMRI Healthy Control Subjects

- Match a randomized subject based on:
  - $\circ$  Age (+/- 2 years)
  - $\circ$  BMI (+/- 2 kg/m^2)
  - Hormonal status

Exclusion criteria for fMRI Healthy Control Subjects

- Any history of psychiatric illness including major depressive disorder, bipolar disorder, psychotic features, or obsessive compulsive disorder, as assessed by SCID
- Current or prior use of any psychiatric medications
- Current or prior substance use disorder
- Unstable medical illness including cardiovascular, hepatic, renal, respiratory, endocrine, neurologic
- Hypothyroidism
- Use of androgens, including testosterone, DHEA and methyltestosterone, within the prior three months
- Abnormal alanine aminotransferase (ALT) or creatinine
- Women who are breastfeeding
- Pregnant women, women who desire to become pregnant, or women of child bearing potential who are not using a medically accepted means of contraception (to include condom, diaphragm, spermicide, intrauterine device, tubal ligation, or partner with vasectomy)
- Additional Routine MRI exclusion criteria as listed below:
  - Cardiac pacemaker
  - Surgical aneurysm clips
  - Neurostimulator
  - Implanted pumps
  - Metal fragments in body / eyes
  - Nitroglycerin patch (if non-removable)
  - Weight >250
  - Severe claustrophobia

Inclusion Criteria for Healthy Controls:

- 1. Female, age 50-75, who provide written informed consent
- 2. Free of lifetime psychiatric medication use
- 3. Postmenopausal, defined as amenorrhea for greater than one year and/or elevated FSH for women with prior hysterectomy

Exclusion Criteria for Healthy Controls:

- 1. Unstable medical illness including cardiovascular, hepatic, renal, respiratory, endocrine, neurologic
- 2. Current or past Axis I psychiatric or substance use disorder (non-prescribed medications, recreational drugs, or alcohol)
- 3. Use of androgens, including testosterone, DHEA and methyltestosterone, within the prior three months

Briefly describe study procedures. Include any local site restrictions, for example, "Subjects enrolled at Partners will not participate in the pharmacokinetic portion of the study." Describe study endpoints.

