# Study visits for randomized subjects

**Screening Visit:** A screening visit will take place to determine eligibility for enrollment. Participants will be asked to complete the MGH ATRQ and sign release of information forms to request documentation from prescribing clinicians. It is estimated that after review of detailed source documents describing past treatment details, 60 women will be confirmed to have partial/nonresponse to antidepressant therapy and be eligible for the randomized, placebo-controlled phase. Screening visit testing will include:

- o complete medical history
- o physical examination, including height and weight
- 0800h Blood draw for ALT, creatinine, CBC, thyroid stimulating hormone (TSH), free testosterone, FSH, urine pregnancy and toxicology
- o diagnostic interview with SCID
- MDD symptom assessment with MADRS
- completion of the MGH ATRQ

If antidepressant-resistance is confirmed following screening procedures, the subject will be scheduled for a baseline visit approximately 1-2 weeks.

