# Baseline Visit for the Randomized, Placebo-Controlled, Augmentation Study: Eligible

subjects will undergo baseline testing immediately before the augmentation phase of the protocol. Baseline visit testing will include the following. However, the blood draw will not be repeated if the Baseline visit occurs within 2 weeks of the screening visit.

- Weight, vital signs, waist-to-hip ratio, and consumptive habits (alcohol, caffeinated beverages) will be recorded
- Urine pregnancy test (for premenopausal women only). Postmenopausal is defined as at least one year since last menses and FSH in the postmenopausal range
- Baseline endocrine blood testing: free testosterone, estradiol, neuroactive steroid panel, DHEAS, blood cortisol, late night salivary cortisol and 8 a.m. salivary cortisol
- o Baseline safety blood testing: ALT, creatinine, CBC
- Depression: MADRS, IDS-SR, CGI-I, S
- Cognitive Functioning: CPFQ
- o Persistent/residual symptom assessment: SF-36, BFI, ESS, FSS, DISF
- Safety assessments: SAFTEE-SI, CHRT, and hirsutism and skin assessments
- We will distribute the Study Drug Compliance and Hot Flash Diary or Menopausal Symptom Diary

• We will also collect DNA to be banked for a future exploratory study into whether androgen receptor CAG repeat length moderates androgen-behavior relationships (based on data by Seidmanet *et al.*).

**Follow-up Visits (Placebo-Controlled Augmentation Phase):** Subjects will then be randomized to receive low-dose testosterone or placebo. Follow-up visits will take place at weeks 2, 4, 6 and 8 post-baseline. Follow up visits will include:

- Urine pregnancy test (for premenopausal women only). Postmenopausal is defined as at least one year since last menses and FSH in the postmenopausal range (weeks 2, 4, 6 and 8)
- Free testosterone levels (weeks 2, 4, 6 and 8)
- Skin evaluations to monitor for side effects (weeks 4 and 8)
- Weight and vital signs will be recorded (weeks 4 and 8)
- Waist-to-hip ratio (week 8)
- Depression: MADRS, IDS-SR, CGI-I, S (weeks 2, 4, 6 and 8)
- Cognitive Functioning: CPFQ (weeks 2, 4, 6 and 8)
- Persistent/residual symptom assessment: SF-36, BFI, ESS, FSS, DISF (weeks 2, 4, 6 and 8)
- Safety: SAFTEE-SI, CHRT (weeks 2, 4, 6 and 8)
- Estradiol levels (weeks 2, 4, 6 and 8)
- Salivary cortisol (week 8)
- Medication management sessions (weeks 2, 4, 6 and 8)
- Neuroactive steroid panel (week 8)

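### Aim 5 does not name its depressed group; if it is the randomized cohort, that cohort is capped on free testosterone while its healthy controls are not, which biases free testosterone in the hypothesised direction

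*Protocol*

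**What the plan says.** **The aim.** Protocol, Specific Aim 5: "Androgen and neuroactive steroid levels will be lower in postmenopausal women with treatment resistant depression than in healthy controls". The aim does not identify the depressed group.

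**The depressed women.** Research Design and Methods describes one depressed cohort, aged 21-75, recruited for the randomized study. Inclusion criterion 2 is "Free testosterone level no higher than the third quartile of the normal range". No numerical ceiling is given, nor whether the range is specific to age or menopausal status. Subject Enrollment reads "A total of 330 women will be enrolled study-wide, of which 100 women with antidepressant-resistant MDD", with the 100 then described as eligible.

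**The controls.** The 30 healthy controls are women aged 50-75 with no lifetime psychiatric medication use. They are postmenopausal by "amenorrhea for greater than one year and/or elevated FSH for women with prior hysterectomy". Their only androgen criterion concerns recent androgen use, which applies to the randomized women as well. Under Healthy control Visits, screening lists no blood draw, and free testosterone is first measured at baseline.

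**The draws in depressed women.** Screening: "0800h Blood draw for ALT, creatinine, CBC, thyroid stimulating hormone (TSH), free testosterone, FSH, urine pregnancy and toxicology". Baseline: "Baseline endocrine blood testing: free testosterone, estradiol, neuroactive steroid panel, DHEAS, blood cortisol", together with salivary cortisol. The baseline section also says that "the blood draw will not be repeated if the Baseline visit occurs within 2 weeks of the screening visit".

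**The analysis.** The SAP covers Aims 1, 2 and 3 only.

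**The concern.** Free testosterone is one of the hormones that Aim 5 compares. If one group is admitted only below a ceiling on it and the other is not, the first group's mean is lower even when depression has no relation to the hormone. The artefact points the same way as the hypothesis, so a finding of lower free testosterone in depressed women could not be separated from the entry criterion. Hormones correlated with free testosterone inherit part of the shift. Because there is no Aim 5 analysis plan, nothing in the documents deals with this.

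The randomized comparison is not at risk. The ceiling applies equally to both arms, so Aims 1-3 are unaffected.

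**Working it through.** The documents give no sample size, error rate, standard deviation (SD) or effect size for Aim 5, so there is no stated figure to reproduce.

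**Inputs from the documents.** 30 controls with no ceiling; depressed women with a ceiling at the third quartile of an unspecified normal range.

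**Assumptions.** Normal values (on the log scale if needed); the same distribution in both groups before the cap; two-sided 5% Welch test; 30 depressed women (number not stated). The cap percentile among postmenopausal women is unknown, so it is varied. The 84th percentile is the case where third quartile means three quarters of the way along a mean ± 1.96 SD range: −1.96 + 0.75 × 3.92 = 0.98 SD.

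**Step 1: shift in the capped group's mean.** For a cap at percentile p with normal quantile c, the shift is −φ(c)/p in SD units. At the 75th percentile, c = 0.674, φ(c) = 0.318 and the shift is −0.318/0.75 = −0.424. A value that correlates r with the eligibility draw shifts by r times this.

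**Step 2: two-sided error with no true difference, 30 v 30** (simulation, 40,000 runs per cell):

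| Cap percentile | Shift, SD | Eligibility value analysed | Redrawn, r = 0.7 | Neuroactive steroid, r = 0.35 |
|---|---|---|---|---|
| 99th | −0.027 | 5% | 5% | 5% |
| 95th | −0.109 | 7% | 6% | 5% |
| 90th | −0.195 | 12% | 8% | 6% |
| 84th | −0.295 | 24% | 13% | 7% |
| 75th | −0.424 | 45% | 22% | 9% |

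At the 75th percentile almost all free testosterone rejections are in the hypothesised direction. With 20 to 50 depressed women, the 75th-percentile figures run from 39% to 51% (eligibility value) and from 19% to 26% (redrawn).

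Both free testosterone columns are needed because the baseline wording may let the screening value stand. That is unclear, since most of the baseline endocrine panel is not in the screening draw.

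The value r = 0.35 is 0.5 (assumed same-draw correlation with free testosterone) × 0.7 (assumed retest correlation). Varying these over 0.2 to 0.7 and 0.5 to 0.9, at the 75th percentile, gives an error of 5% to 18%.

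**Step 3: would capping the controls as well cure the neuroactive steroid comparison?** Assume depressed women are truly 0.5 SD lower on both hormones, with a cap at the controls' 75th percentile.

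- Depressed women: the cap lies 0.674 + 0.5 = 1.174 SD above their own mean. φ/Φ = 0.200/0.880 = 0.227, and the shift is 0.35 × 0.227 = 0.08.
- All controls kept: expected difference 0.50 + 0.08 = 0.58 SD.
- Controls restricted to the same ceiling (same-draw correlation 0.5): their mean falls by 0.5 × 0.424 = 0.21, so the expected difference is 0.58 − 0.21 = 0.37 SD.

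About 30 × 0.25 = 7.5 controls are lost. With 22 left, power is 27%, against 48% for an unselected 30 v 30 comparison. The restricted estimate is 0.13 SD too low for the population difference; the unrestricted one is 0.08 SD too high. At the 90th percentile the two estimates are 0.43 and 0.53 SD.

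**Step 4: extra women needed if screening values are used.** Per 30 admitted, under the null: 30/0.75 − 30 = 10; 30/0.836 − 30 = 6; 30/0.90 − 30 = 3; 30/0.95 − 30 = 2 (rounded).

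**The case against.** The strongest reply is that the premise is inferred. Aim 5 never says that the randomized women are its depressed group. The enrolment paragraph counts 330 women as enrolled and only 100 depressed women as eligible, and free testosterone is drawn at screening. Using all screened depressed women is therefore not ruled out and would avoid the bias for that hormone. This stands: the bias is conditional. But the plan does not say so, and the escape does not extend to neuroactive steroids. That panel is listed for depressed women only from the baseline visit on, after the cap has been applied.

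The second reply is that the size is undetermined. This also stands. If the normal range extends well above usual postmenopausal values, the cap excludes few women and the error stays near 5%. A reader might take the 45% figure as the trial's error rate. The documents do not support that: it needs the cap at the 75th percentile of postmenopausal women and the eligibility value itself as the analysed value, and neither is stated.

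Third, a reader might infer that criterion 2 is an error or that it compromises the trial. It does neither. It is an entry rule applied alike to both randomized arms.

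Finally, Aim 5 is an observational comparison, and the outcome measures listed under Study Design relate to Aims 1-3. That limits the weight of the point. Still, Aim 5 is a numbered aim with a directional hypothesis and its own recruited controls, separate from the aim labelled exploratory.

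**Conclusion.** The concern holds conditionally. The documents establish that the Aim 5 depressed group is unnamed, that the only depressed cohort described is capped on free testosterone, that the controls are not, and that no Aim 5 analysis exists. If that cohort is used as it stands, the direction of the selection bias is fixed and favours the hypothesis. Its size is not fixed: it runs from negligible to large, depending on the cap percentile, on whether the value is redrawn, and on the number of postmenopausal depressed women. For neuroactive steroids it is smaller, about 6% to 9% error for caps at the 90th to 75th percentile at r = 0.35, and more if the correlation is higher.

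It should be fixed before Aim 5 is analysed. A reader might infer that capping the controls as well settles the matter. Step 3 shows why that should not be the main analysis: it can understate a real difference by more than the uncorrected comparison overstates it.

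**What to change.** Add an Aim 5 analysis section that does the following.

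1. Name the depressed group, and state the numerical ceiling, its reference range and the draw times. The depressed women's screening draw is fixed at 0800h; the controls' draw has no stated time.
2. For free testosterone, compare the screening values of all screened postmenopausal depressed women who meet the other criteria, including those excluded only by criterion 2, with all controls.
3. For neuroactive steroids and other hormones drawn only at baseline, keep the comparison with all controls and state that the ceiling biases it toward the hypothesis. Add a sensitivity analysis limited to controls at or below the same ceiling, and report how many exceed it. It should not replace the main comparison, and a null result in it is weak evidence.

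**Cost.** No new draws and no change to eligibility. Item 2 means keeping the screening data of women who fail only criterion 2 and completing their treatment-history check, since eligibility is confirmed "after review of detailed source documents describing past treatment details" and that work might otherwise stop once they are ineligible. Under the null this is about 2 to 10 extra women per 30 admitted, for caps from the 95th to the 75th percentile.

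**What remains.** The depressed women all take antidepressants, the controls have never taken psychiatric medication, and these controls are not matched on age or BMI. Handling the ceiling leaves Aim 5 an association.

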# fMRI Healthy Control Substudy Visits

Screening visit: A screening visit will take place to determine eligibility for enrollment and ensure that subjects meet inclusion and exclusion criteria. Twenty women with no history of depression or other psychiatric illness will be eligible for the baseline fMRI scan. Screening visit testing will include:

- Complete medical history
- Diagnostic interview with SCID
- Physical examination, including height and weight
- o Morning blood draw for ALT, creatinine, CBC, thyroid stimulating hormone (TSH),

Partners Human Subjects Research Application Version Date: June 1,

Form 2005

free testosterone, FSH, and urine pregnancy test

If a subject is found to be eligible following screening procedures, the subject will be scheduled for the baseline fMRI visit in approximately 1-2 weeks.

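### The depressed fMRI women have a free-testosterone ceiling and the fMRI healthy controls have none stated, so the exploratory case-control androgen comparison should use a common range.

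*Protocol*

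**What the plan says.** - **Depressed women.** The inclusion list for randomized subjects (Protocol, RESEARCH DESIGN AND METHODS) requires "Free testosterone level no higher than the third quartile of the normal range". The fMRI substudy adds only MRI-related exclusions for a subset of 20 randomized women, so the ceiling carries over to them.
- **fMRI healthy controls (n=20).** The inclusion rule in the same section is "Match a randomized subject based on" three factors: age within 2 years, BMI within 2 kg/m², and "Hormonal status". The first two have tolerances. The third has no definition, named hormone or tolerance.
- **Androgen-related exclusion for these controls.** The only one is "Use of androgens, including testosterone, DHEA and methyltestosterone, within the prior three months", which also applies to the randomized women and concerns exogenous androgens.
- **Control screening** (Protocol, fMRI Healthy Control Substudy Visits). The blood draw includes "free testosterone, FSH, and urine pregnancy test", but no eligibility limit is tied to the testosterone result.
- **Use of the two groups** (Protocol, SPECIFIC AIMS, Exploratory Aim). "We will investigate androgen and other hormonal correlates of functional and structural neuroanatomy in women with treatment resistant depression", in comparison with healthy women, as preliminary data for later studies.
- **Analysis.** The SAP covers Aims 1 to 3. It gives no method for the fMRI, exploratory or Aim 5 comparisons.

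**The concern.** Free testosterone is one of the exposures under study in the exploratory aim, and the two groups are selected differently on it. Cutting off the upper tail in one group lowers that group's mean, shrinks its spread, and pulls any correlation with a brain measure towards zero. Each of these can look like an effect of depression when it comes only from eligibility. The sponsor intends to build later studies on these results, so an artefact could be carried forward.

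The issue reaches beyond the fMRI substudy. Specific Aim 5 predicts lower androgen levels in depressed postmenopausal women than in healthy postmenopausal controls, and that separate control list (age 50 to 75) has no free-testosterone limit either. The protocol does not say where the Aim 5 cases come from. If they are randomized women, the ceiling pushes the result in the predicted direction.

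**Working it through.** The plan gives no effect size, power or sample-size argument for this comparison, so there is no figure to reproduce. The eligibility lists establish the asymmetry; the arithmetic below only gauges its size.

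**Inputs.** From the protocol: 20 depressed women with the ceiling and 20 controls with none stated. Assumed: both source populations follow the same standard normal distribution of free testosterone, the ceiling is its 75th percentile (c = 0.674), and tests are two-sided at 5%.

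**1. Mean and spread after truncation.** With λ = φ(c)/Φ(c) = 0.3178/0.75 = 0.424:
- mean shift = −λ = −0.42 SD
- variance = 1 − cλ − λ² = 1 − 0.286 − 0.180 = 0.535, so the SD ratio u = 0.73

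**2. Controls above the ceiling.** Expected 0.25 × 20 = 5. The chance of none is 0.75^20 = 0.3%.

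**3. Correlation in the depressed group.** r′ = r·u / √(1 − r² + r²u²).

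**4. False-positive rate for a difference in correlations.** On the Fisher-z scale, SE = √(1/17 + 1/17) = 0.343.

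| True r | r′ in cases | Difference in z | Difference / SE | Chance of p < 0.05 |
|---|---|---|---|---|
| 0.3 | 0.22 | 0.082 | 0.24 | 5.7% |
| 0.5 | 0.39 | 0.139 | 0.40 | 6.9% |
| 0.7 | 0.58 | 0.201 | 0.59 | 9.0% |

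Simulation agrees (5.7%, 7.0%, 9.0%).

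**5. Linear slopes.** Selecting on the predictor leaves a linear slope unbiased. In simulation the slopes with and without truncation were equal (0.50 and 0.50; 0.70 and 0.70). The cost is precision: the standard error in the truncated group is about 1/0.73 = 1.37 times as large.

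**6. Mean free testosterone, 20 against 20.**
- pooled SD = √((1 + 0.535)/2) = 0.876
- standardised difference = 0.424/0.876 = 0.484
- noncentrality = 0.484 × √(20/2) = 1.53
- chance of a false difference = P(Z > 1.96 − 1.53) = 33%; simulated t-tests give 31%
- with the ceiling applied to both groups (20 against 15) the simulated rate is 5%

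**7. Sensitivity to the assumptions.**
- If the third quartile means 75% of the way along a central-95% range, c = −1.96 + 0.75 × 3.92 = 0.98. The shift is then 0.30 SD, u = 0.79, and r = 0.5 becomes about 0.42. The false difference in means occurs about 18% of the time by the normal approximation and 16% to 17% in simulation.
- If levels are right-skewed (lognormal, log-SD 0.5 to 0.8), u is 0.47 to 0.31 and r = 0.5 becomes 0.26 to 0.18.
- If depressed women's levels really are 0.5 SD lower, the ceiling removes P(Z > 0.674 + 0.5) = 12% of them rather than 25%, and its effect is smaller.

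**The case against.** **The harm is small for the comparison actually stated.** The exploratory aim is about correlates of neuroanatomy. With 20 per group the attenuation is about a quarter to three-fifths of the standard error of the difference, and a slope-based analysis would avoid it if the relation is linear. This stands. A reader might infer that a weaker correlation in depressed women is to be expected as an observed finding. The figures do not support that: sampling error dominates.

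**The mean-level problem belongs to another aim.** This is also right. The exploratory aim states no hypothesis about mean levels; Aim 5 does, with a different control group. A change to the fMRI list alone would leave Aim 5 untouched, so the fix has to name it.

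**Matching may already close the gap.** Every matched case lies at or below the ceiling, and "Hormonal status" could be meant to include testosterone. It could equally mean menopausal status. It is therefore too strong to call the controls unrestricted; the documents support only that no ceiling is stated.

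**The ceiling is an entry criterion for a testosterone trial, and controls receive no drug.** That explains why the lists differ. It does not make the groups comparable on free testosterone.

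**The size is uncertain.** It is. The protocol does not define the third quartile of the normal range or say whether it is age-specific. The ceiling also concerns free testosterone only, while the aim covers other hormones too.

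**Conclusion.** The point holds as a minor, inexpensive improvement. The two fMRI groups are selected differently on free testosterone, and no written analysis allows for it.

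Under one shared normal distribution cut at the 75th percentile, the depressed group's mean is 0.42 SD lower, its SD is 0.73 of the controls', and correlations of 0.3, 0.5 and 0.7 appear as 0.22, 0.39 and 0.58. The practical consequence depends on the analysis: slight for a difference in correlations, none in bias for linear slopes, and material for mean free testosterone, where about 30% of comparisons would be falsely significant (under 20% on the milder reading of the ceiling). Right skew would make the attenuation of correlations worse; truly lower levels in depressed women would make the ceiling matter less.

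A reader might also infer that the efficacy or safety results are compromised. They are not: Aims 1 to 3 compare randomized arms that share the same ceiling. For Aim 5 the conclusion is conditional on its cases being randomized women, which the protocol does not state.

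**What to change.** 1. Run the case-control androgen analyses on the common range: include only fMRI controls whose screening free testosterone meets the ceiling used for the randomized women. Use the screening value, because the cases were selected at screening. Alternatively, add the same ceiling to the fMRI control inclusion list.
2. Compare groups through a group-by-hormone regression (slopes), not through separate correlations. The common range also guards against a relation that is not linear across the full range.
3. State whether hormonal status includes testosterone and, if so, with what tolerance. Define the third quartile of the normal range, including whether it is age-specific.
4. For Aim 5, state where the cases come from. If they are randomized women, apply the same restriction, using the free testosterone measured at the healthy controls' baseline visit (Protocol, Healthy control Visits).
5. Write these analyses into the SAP.

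**Cost.** No new test is needed. Under the 75th-percentile assumption about 5 of 20 fMRI controls leave the analysis, and the standard error for comparing correlations rises from 0.343 to √(1/17 + 1/12) = 0.377. If the ceiling becomes an inclusion criterion instead, about 20/0.75 = 27 otherwise eligible controls are needed to obtain 20.
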